## Protocol Synopsis

Study Title:	The HepQuant SHUNT Test for Monitoring Liver Disease and Treatment Effects by Measuring Liver Function and Physiology		
Sponsor:	HepQuant LLC		
Device:	HepQuant SHUNT Liver Diagnostic Kit		
Funding BY:	HepQuant LLC		
Device Provided by:	HepQuant LLC		
Protocol:	ID:	HQ-US-SHUNT-1701	
	Version:	Original Version 5.0	
		Amended Version 6.0	
	Date:	Original date September 5, 2017	
		Amendment date May 15, 2018	
Compounds used in HepQuant SHUNT Test Kit:	[24-  C]cholic acid (13C-cholate or 13C-CA)		
	[2,2,4,4-  H(d4)]cholic acid (d4-cholate or d4-CA)		
Indication for Use:	Monitoring effects of Liver Disease and Treatment on Liver Function		
Gilead Parallel Clinical Trials:	GS-US-384-1943 (STELLAR 3) / Gilead Sciences:	IND 129570	
	GS-US-384-1944 (STELLAR 4) / Gilead Sciences;	IND 129570	
	GS-US-454-4378 (NASH F3/F4) / Gilead Sciences;	INDs pending	
Drug used in the Parallel Drug Trials:	Selonsertib, GS-0976, and GS-9674		
IDE Numbers (for use of the HepQuant SHUNT Test Kit in subjects co-enrolled in the Parallel Drug Trials):	G170034-S001 for GS-US-384-1943 (STELLAR 3)		
	G170034-S002 for GS-US-384-1944 (STELLAR 4)		
	IDE pending for GS-US-454-4378 (NASH F3 / F4)		
Study Centers/Pis:	This HepQuant SHUNT study is run in parallel to three Gilead clinical trials. Subjects are simultaneously participating in this HepQuant SHUNT study while participating in a Gilead-sponsored clinical trials for treatment of NASH. Because the HepQuant study will focus on the subjects with more advanced liver disease, the clinical sites participating in the HepQuant study must also be participating in one of the NASH F3 (STELLAR 3), NASH F4 (STELLAR 4), or GS-US-454-4378 (NASH F3 and F4) studies. The maximum number of clinical sites is 15 and the maximum number of study subjects is 100.		

Primary Objective:	To determine the utility of the Disease Severity Index (DSI) from the HepQuant SHUNT test for monitoring liver disease and treatment effects, DSI and the change in DSI ( $\Delta$ DSI) will be measured across all treatment arms.	
	The clinical significance of $\Delta$ DSI will be evaluated by analyzing the relationships of $\Delta$ DSI to changes in standard laboratory tests, clinical models, histologic stage of disease, and risk for clinical outcome.	

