	We will also evaluate whether the HepQuant SHUNT test and DSI identify a treatment effect in the combined NASH F3 + NASH F4 cohorts, after unblinding of treatment assignments and completion of the primary analysis for Gilead's clinical trials. Treatment effect, as measured by DSI and $\Delta$ DSI, will be defined from the differences in DSI between treatment and placebo arms; and, compared to the treatment effect defined by changes in histology, standard laboratory tests, clinical models and by clinical outcomes.	
Secondary Objectives:	To determine the ability of baseline DSI, performed prior to treatment, to assess the severity of liver disease by: 1. correlation with other baseline tests of liver disease severity; and, 2. prediction of risk for future clinical outcome.	
Study Design:	Open Label HepQuant SHUNT Testing in All Subjects	
	STELLAR 3:	Baseline and Weeks 24, 48, and 240
	STELLAR 4:	Baseline and Weeks 24, 48, and 240
	GS-US-454-4378 (NASH F3 / F4):	Baseline and Weeks 24 and 48
Subjects, N:	Up to a total of 100 for all trials	
Clinical Sites, N:	Up to 15	
Target Populations:	NASH F3:	NASH Clinical Research Network (CRN) Fibrosis Stage 3
	NASH F4:	NASH CRN Fibrosis Stage 4 (compensated cirrhosis)
Compounds used in HepQuant SHUNT Test Kit:	[24-  C]cholic acid, 20 mg, intravenous injection	
	[2,2,4,4-  H(D)]cholic acid, 40 mg, oral solution	
Drug Treatment:	STELLAR 3:	Selonsertib vs Placebo
	STELLAR 4:	Selonsertib vs Placebo
	GS-US-454-4378 (NASH F3/F4):	Selonsertib, GS-0976, GS-9674 alone or in combination versus placebo.
Duration of Drug Treatment:	STELLAR 3:	240 weeks
	STELLAR 4:	240 weeks
	GS-US-454-4378 (NASH F3/F4):	48 weeks
Duration of Study and Drug Trial:	STELLAR 3:	252 weeks
	STELLAR 4:	252 weeks
	GS-US-454-4378 (NASH F3/F4):	52 weeks

Diagnostic and Eligibility Criteria:	Enrollment in the corresponding Gilead Trial, listed above
	Intravenous access for catheter placement
	Able to take orally administered solution
	No known allergy to any component of the HepQuant SHUNT test kit
Procedures and Frequency of the HepQuant SHUNT Testing:	
STELLAR 3:	Baseline and Weeks 24, 48, and 240
STELLAR 4:	Baseline and Weeks 24, 48, and 240
GS-US-454-4378 (NASH F3/F4):	Baseline and Weeks 24 and 48
Dose and Mode of Administration of Drug used in Drug Trial:	
STELLAR 3 and 4:	Selonsertib 6 or 18 mg orally daily

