## 8.2 Primary Objective

### 8.2.1 Outline of Approach

The primary objective is to determine the utility of the Disease Severity Index (DSI), derived from the HepQuant SHUNT test, for monitoring liver disease and treatment effects.

- Utility will be defined by measuring DSI and the change in DSI ( $\Delta$ DSI) across all treatment arms.
- The clinical significance of a change in DSI will be evaluated by analyzing the relationships between changes in DSI and changes in histologic stage of disease, clinical models, and risk for clinical outcome.

Treatment effect will be determined after the completion of the clinical trial and after completion of Gilead's analysis of the results of the main clinical trial. Treatment effect will be defined from the difference in  $\Delta$ DSI between treatment and placebo arms. Treatment effect defined by  $\Delta$ DSI will also be compared to the treatment effect defined by changes in other tests and by clinical outcomes.

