### 8.2.3 Statistical Considerations

Our Primary Objective is to determine the utility of the Disease Severity Index (DSI), derived from the HepQuant SHUNT test, to monitor liver disease and treatment effects. We propose a three-step analytical process to achieve this goal:

- First, without knowledge of treatment arm and for the group of subjects as a whole, we will track DSI and the change in DSI,  $\Delta$ DSI, from baseline to on-treatment and follow-up timepoints.
- Second, we will apply separate survival models to evaluate  $\Delta$ DSI as a continuous variable and a 2 point or more drop in DSI as dichotomous variable in the prediction of changes in other tests or models of liver disease severity and clinical outcomes.
- Third, after unblinding the study and completion of Gilead's analysis of the main clinical trial, we will make request of Gilead for allocation code to determine if there is a treatment effect, by comparing the difference between the  $\Delta$ DSI of the treatment arm versus the  $\Delta$ DSI of the placebo arm. The significance of this difference will be evaluated using two-sided t-tests and survival models.

Due to short enrollment period, only 5 STELLAR 3 and 4 STELLAR 4 subjects were enrolled into HQ-SHUNT-1701. STELLAR 3 and STELLAR 4 had two treatment arms (6 and 18 mg/d doses) and one placebo arm. Of the 9 subjects enrolled in HQ-SHUNT-1701, we would project that 6 would have been treated with selonsertib and 3 would have been taking placebo. Enrollment criteria, diagnosis, and F3/F4 stage of NASH is identical between the STELLAR studies and Gilead 454-4378. For the final analysis of treatment effects, once the code on all treatment arms from all studies is unblinded the projected 6 cases enrolled in HQ-SHUNT-1701 on selonsertib treatment from STELLAR studies will be added to the cases from Arm C of 454-4378 (selonsertib monotherapy) and the projected 3 cases enrolled in HQ-SHUNT-1701 on placebo from STELLAR studies will be added to the cases from Arm F (placebo) of the 454-4378 study.

Furthermore, we will link treatment effect defined by the change in DSI to effects of treatment on other tests and clinical outcomes (bleeding from varices or portal hypertensive gastropathy, ascites, encephalopathy, SBP, progression to cirrhosis, and

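### Section 8.2.3 defines the groups for the final treatment-effect analysis only for selonsertib monotherapy versus placebo, and does not say how the other active arms of 454-4378 enter the test

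*Combined protocol and SAP*

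**What the plan says.** The Synopsis states that DSI and its change "will be measured across all treatment arms", and Section 8.2.1 likewise defines utility by measurement "across all treatment arms". The Synopsis adds that treatment effect "will be defined from the differences in DSI between treatment and placebo arms", without naming a drug. Section 5.3.1 lists the regimens of GS-US-454-4378 as selonsertib, GS-0976 and GS-9674 singly, combinations of them, and placebo.

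Step three of Section 8.2.3 compares change in DSI in the treatment arm (singular) with the placebo arm: "The significance of this difference will be evaluated using two-sided t-tests and survival models". The next paragraph reports that "only 5 STELLAR 3 and 4 STELLAR 4 subjects were enrolled into HQ-SHUNT-1701". It projects six of these nine on selonsertib and three on placebo. For the final analysis of treatment effects it adds the six to Arm C, described as selonsertib monotherapy. The three placebo cases "will be added to the cases from Arm F (placebo) of the 454-4378 study".

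The section ends with GEE and profile analyses of treatment versus placebo groups. Section 9.0 compares the treatment arms (plural) with placebo. No section assigns the GS-0976, GS-9674 or combination arms to a contrast, says whether active arms are pooled, or addresses multiple comparisons.

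**The concern.** A multi-arm trial has no single treatment arm. From this text, one analyst could test Arm C plus STELLAR selonsertib only, another could pool every active arm, and a third could test each regimen separately. All three would comply with the plan. These are different questions, since Section 3.2 describes three drugs with different mechanisms, and they may give different answers on whether DSI detects a treatment effect.

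Timing makes the gap matter more. Sections 2.1 and 8.2.3 place the comparison after unblinding and after the parent trials' main analyses, when the regimens that performed well will already be known. A contrast still open at that point can be chosen with results in hand.

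The specified t-test is also unadjusted, although the groups combine subjects from different trials and fibrosis stages, and the projected 2:1 STELLAR split need not match the ratio of Arm C to Arm F.

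**Working it through.** **Inputs from the documents.** Maximum enrolment 100 (Synopsis). Nine STELLAR subjects, projected 6 selonsertib and 3 placebo (8.2.3). SD of change in DSI 3.5, with 3 and 4 used in the table; alpha 0.05; target difference of 2 to 3 points (8.1). Two-sided test (8.2.3).

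**Assumptions.** Enrolment reaches 100 with no dropout, and 454-4378 has k equal arms. Three single agents, at least one combination and placebo make k at least 5. The labels C and F suggest six or more, so k is taken from 5 to 7.

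**1. The plan's own figures.** Power is from the noncentral t, with SE = SD × √(1/n1 + 1/n2), noncentrality = difference/SE and df = n1 + n2 − 2. For 29 per arm, difference 2 and SD 3: SE = 3 × √(2/29) = 0.788 and noncentrality = 2.54. The one-sided critical value 1.673 gives 0.80590, the tabled figure. The two-sided value 2.003 gives 0.70. All 12 rows of the table match a one-sided test; two-sided power at the same sizes is 0.66 to 0.74. That is a separate matter, but it means the table cannot be read across to the planned test. Everything below is two-sided.

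**2. Group sizes and power, N = 100, SD 3.5.** Each 454-4378 arm has (100 − 9)/k subjects. The named comparison is Arm C + 6 versus Arm F + 3.

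| k | Per arm | Named comparison | Outside it | Power, 2 points | Power, 3 points | All active v placebo | Its power, 2 points |
|---|---|---|---|---|---|---|---|
| 5 | 18 | 24 v 21 | 55 | 0.46 | 0.80 | 79 v 21 | 0.63 |
| 6 | 15 | 21 v 18 | 61 | 0.41 | 0.74 | 82 v 18 | 0.58 |
| 7 | 13 | 19 v 16 | 65 | 0.37 | 0.69 | 84 v 16 | 0.55 |

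For k = 6: SE = 3.5 × √(1/21 + 1/18) = 1.124, noncentrality = 2/1.124 = 1.78 and power = 0.41. Over SD 4 to 3 this is 0.33 to 0.52, and the pooled figure is 0.48 to 0.72. At the 60 subjects cited in Section 8.1, the named comparison is 16 v 13, 14 v 11 or 13 v 10, and power for 2 points is 0.25 to 0.32.

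**3. Dependence on allocation.** If Arms C and F hold a share s of the 91 subjects from 454-4378, then 91 × (1 − s) are outside. More than half of 100 are outside only if s < 1 − 50/91 = 0.45. Equal arms with k = 5 to 7 give s = 0.40 to 0.29. With a quarter in each of C and F, 45 are outside.

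**4. Pooling can reverse.** The pooled power assumes that every regimen lowers DSI by the same 2 points. For 82 v 18, SE = 3.5 × √(1/82 + 1/18) = 0.911. If only the 21 selonsertib subjects respond, the average effect is 2 × 21/82 = 0.51, noncentrality is 0.56 and power is about 0.09. Pooled power equals the named comparison's 0.41 when the average effect is about 1.6, that is when the other 61 subjects average (1.6 × 82 − 2 × 21)/61 = 1.46 points.

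**5. Trial mix.** For k = 6, STELLAR subjects make up 6/21 = 29% of the selonsertib group and 3/18 = 17% of the placebo group, so an unadjusted test lets differences between trials into the treatment contrast.

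**The case against.** A reader might infer that selonsertib versus placebo is the only treatment-effect test planned and that the other arms are excluded. The text does not support that. Step three of 8.2.3, the Synopsis, the GEE and profile analyses and Section 9.0 all describe treatment versus placebo without naming a drug. The Arm C and Arm F sentence can be read as a rule for placing nine STELLAR subjects. STELLAR had no GS-0976, GS-9674 or combination arm, so that rule had no reason to mention them.

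A reader might also infer that most co-enrolled subjects never enter a treatment comparison. The documents do not establish this either: arm sizes are not given, no arm is excluded, and steps one and two of 8.2.3 carry no restriction by arm. It is also fair that measuring DSI in all arms does not promise a test for each, and that added contrasts in arms of about 15 subjects would have low power.

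These points limit the claim but do not close the gap. The general wording names no arms and varies between singular and plural. Reading the sentence as a placement rule leaves the treatment contrast undefined for every regimen other than selonsertib monotherapy.

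**Conclusion.** The concern holds as a gap in specification: group composition is defined for one regimen against placebo, and the other active arms have no stated role in the treatment-effect test. This follows from the text alone.

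The size is conditional. With 100 subjects, five to seven equal arms in 454-4378 and the projected 6:3 STELLAR split, 55 to 65 subjects fall outside the named comparison. Its two-sided power for 2 points at SD 3.5 is 0.37 to 0.46, and lower if enrolment stops short of 100. If Arms C and F hold about 45% or more of the 454-4378 subjects, no more than half fall outside.

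It would also go too far to say that pooling is simply the better analysis. The rise from 0.41 to 0.58 in the six-arm case depends on similar effects across regimens, which the documents do not show. The change should be made before unblinding.

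**What to change.** Replace the unadjusted t-test with one linear model for Week 48 change in DSI, with terms for every arm, baseline DSI, F3/F4 stage and parent trial. With nine STELLAR subjects, STELLAR versus 454-4378 is enough for the trial term, since stage already separates STELLAR 3 from STELLAR 4. State how the two STELLAR selonsertib dose groups are coded alongside Arm C.

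Keep selonsertib monotherapy versus placebo as the named contrast. Add each other regimen versus placebo, and pooled active versus placebo, as contrasts labelled supportive and reported with confidence intervals. State that any power gain from pooling depends on similar effects and could reverse. Align the Synopsis, 8.2.1 and 8.2.3, and use the same arm definitions for the GEE and profile analyses.

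The cost is SAP wording and a few supportive contrasts. No new subjects, visits or measurements are needed. Because Section 2.1 has the parent-trial sponsor conduct these analyses, the specification should also go into the analysis request to that sponsor before the codes are released.

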**Statistical Methods:**

We will determine the utility of the Disease Severity Index (DSI) from the HepQuant SHUNT test to monitor liver disease and treatment effects by measuring liver function and physiology. We propose a three-step analytical process to achieve this goal. First, without knowledge of treatment arm, we will track DSI and the change in DSI,  $\Delta$ DSI, from baseline to on-treatment and follow-up timepoints. Second, we will apply separate survival models to evaluate  $\Delta$ DSI as a continuous variable and a 2 point or more change in DSI as dichotomous variable in the prediction of changes in other tests or models of liver disease severity and clinical outcomes. In HCV, an increase in DSI of 2 or more has been associated with disease progression; and, a decrease in DSI of 2 or more has been associated with improvement after viral clearance. Third, once the treatment arms have been unblinded we will evaluate if the use of the HepQuant SHUNT test and DSI identify a treatment effect in the combined cohort of NASH F3 plus NASH F4; and we will compare DSI to the primary measures of efficacy in each of the clinical trials. In terms of DSI, a treatment effect will be defined from the difference between the  $\Delta$ DSI of the treatment arm versus the  $\Delta$ DSI of the placebo arm. The significance of this difference will be evaluated using a two-sided t-test. Furthermore, we will link treatment effect defined by DSI to effects of treatment on other tests and clinical outcomes (bleeding from varices or portal hypertensive gastropathy, ascites, encephalopathy, SBP, progression to cirrhosis, and patient mortality or liver transplantation). We will use both generalized estimating equations (GEE) and profile analysis – profile of DSI between treatment and placebo groups at each time point – for additional primary endpoint analyses.

We will also determine the ability of baseline DSI, performed prior to treatment, to assess the severity of liver disease by: 1. correlation with other baseline tests of liver disease severity; and, 2. prediction of risk for future clinical outcome.

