### 5.3.2 Timing of HepQuant SHUNT testing

The basic design for HepQuant SHUNT testing is similar across the clinical trials:

[figure not shown]
- In all trials, the HepQuant SHUNT Test is initially performed at baseline, prior to any treatment, to assess liver function and physiology at entry to the trial, time  $t_0$ .

- The HepQuant SHUNT Test is then performed serially to monitor the change in function and physiology, relative to baseline, during the placebo/treatment and post-treatment follow-up periods of the study. In all cases, the study visits for the HepQuant tests will coincide and align with the protocol-defined visit windows for the GILEAD clinical trials.

In the STELLAR 3 and STELLAR 4 trials, the HepQuant SHUNT test will be administered at baseline and Weeks 24, 48, and 240. The total length of time subject will be in the SHUNT study is approximately 252 weeks. The study design for the STELLAR studies is shown in the figure below.

In the GS-US-454-4378 (NASH F3/4) trial, the HepQuant SHUNT test will be administered at baseline and Weeks 24 and 48. The total length of time subject will be in SHUNT study is 52 weeks. The study design for the GS-US-454-4378 (NASH F3/4) trial is shown in the following figure.

The specific comparative data collected in the HepQuant study are given in Appendix C. The results of the HepQuant SHUNT test will be transferred to Gilead who will analyze the test results in comparison to other procedures and clinical outcomes recorded in the Gilead trials. HepQuant will query Gilead for the results of these analyses.

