## **8.0 Data Analysis and Statistics**

### **8.1 Sample Size Calculation**

An important offshoot of our prior serial studies of the HepQuant SHUNT test was defining an average standard deviation for  $\Delta$ DSI (average SD of  $\Delta$ DSI = 3.5) that could

be used to determine sample sizes. The following table demonstrates the sample sizes required to detect a range of changes in DSI at 80% power or higher – for the case of the NASH trials. A sample size of 60 total subjects (N in following table), well below the size of our projected number of evaluable NASH patients could provide sufficient power to detect a difference in the  $\Delta$ DSI of 2 to 3.

Actual Power	N1	N2	N	<math>\Delta</math>DSI	<math>\sigma</math>	Alpha
0.80010	112	112	224	1.00	3.00	0.050
0.80084	199	199	398	1.00	4.00	0.050
0.80590	29	29	58	2.00	3.00	0.050
0.80590	51	51	102	2.00	4.00	0.050
0.82409	14	14	28	3.00	3.00	0.050
0.80486	23	23	46	3.00	4.00	0.050
0.81316	8	8	16	4.00	3.00	0.050
0.82409	14	14	28	4.00	4.00	0.050
0.85055	6	6	12	5.00	3.00	0.050
0.81383	9	9	18	5.00	4.00	0.050
0.80153	4	4	8	6.00	3.00	0.050
0.84086	7	7	14	6.00	4.00	0.050

NOTE: Once the treatment for the clinical trial is unblinded, if DSI is unchanged or worsens by 1 in the placebo arm, then one could detect as little as a 1 or 2 point reduction in DSI by selonsertib in the treatment arm.

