patient mortality or liver transplantation). In addition, we will use both generalized estimating equations (GEE) and profile analysis – profile of DSI between treatment and placebo groups at each time point – for additional primary endpoint analyses. The two NASH trials will be combined in the analysis of treatment effect.

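### Section 8.2.3 puts four unranked methods and no named visit behind the DSI treatment effect; if any one positive result counted, the false-positive chance would be roughly 7–14% under stated assumptions, not 5%

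*Combined protocol and SAP*

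**What the plan says.** The third analytical step in Section 8.2.3 compares change in DSI between treatment and placebo once the code is broken: "The significance of this difference will be evaluated using two-sided t-tests and survival models". The closing paragraph of the same section adds GEE and a profile analysis of DSI by group at each time point, "for additional primary endpoint analyses".

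The Statistical Methods part of the synopsis describes the same step differently: "The significance of this difference will be evaluated using a two-sided t-test". It mentions no survival model for the arm comparison, and it also calls GEE and profile analysis additional.

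Neither place names a visit. The synopsis criteria for evaluation define the treatment effect at a generic time point i. Under Section 5.3.2, for the STELLAR trials, "the HepQuant SHUNT test will be administered at baseline and Weeks 24, 48, and 240"; GS-US-454-4378 tests at baseline and Weeks 24 and 48. Section 8.2.3 reports that only 5 STELLAR 3 and 4 STELLAR 4 subjects were enrolled, so at most 9 people can contribute at Week 240.

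The only significance level in the document is the 0.050 column of the Section 8.1 table. There is no order of testing, multiplicity adjustment or success criterion.

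**The concern.** Four methods and at least two visits address one question, and nothing says which result answers it. An analyst who has seen the unblinded data could report whichever combination favours DSI, and the 5% level would then not describe the risk of a chance finding. The reverse problem is as real: if the t-test at Week 24, the t-test at Week 48 and the GEE disagree, the plan cannot say what the study found.

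This matters because Section 9 hopes the overall results will support the test as a tool, or even an endpoint, in future drug trials. It is sharper because the analyst is not settled: Section 2.1 assigns the treatment-effect analyses to Gilead, while in Section 8.2.3 the sponsor requests the allocation code to make the comparison.

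**Working it through.** **1. The plan's own figure.** The document gives no overall error rate, so the only figure to reproduce is power in Section 8.1. Take the row for a difference of 2, SD 3 and 29 per arm: "0.80590 29 29 58 2.00 3.00 0.050". The noncentrality is 2 / (3 × √(2/29)) = 2.54 on 56 degrees of freedom. A one-sided 0.05 test gives power 0.80590, matching the table; a two-sided 0.05 test gives 0.7036. So the tabulated alpha is one-sided while the planned t-test is two-sided. That is a separate matter, but it means Section 8.1 does not fix the level of the treatment comparison either.

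**2. Simple upper reference.** For k independent tests at 0.05, P(at least one positive) = 1 − 0.95^k:
- k = 2: 9.75%
- k = 3: 14.3%
- k = 4: 18.6%

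These overstate the problem here, because every test uses the same subjects' DSI values.

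**3. Null simulation with correlated data.**

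Inputs from the document:
- average SD of change in DSI 3.5 (Section 8.1)
- visits at Weeks 24 and 48 (Section 5.3.2)
- two-sided tests (Section 8.2.3)
- a drop of 2 points or more, used here as the survival event (Section 8.2.3 defines it only as a predictor)

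Assumptions, not in the document:
- *Correlation between the Week 24 and Week 48 changes:* 0.3 to 0.9.
- *Arm sizes:* 30 v 30 follows the total of 60 in Section 8.1. 50 v 50 is the 100-subject cap split in two. 21 v 18 takes the cap less 9 STELLAR subjects, spread evenly over six presumed arms (91/6 ≈ 15), plus the projected 6 selonsertib and 3 placebo STELLAR subjects.
- *Test forms:* pooled t-test at each visit; GEE as the time-averaged difference with a small-sample reference; profile analysis as Hotelling T²; survival as a log-rank test on time to the 2-point drop.

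With 40,000 null trials per setting, the Monte Carlo standard error near 5% is √(0.05 × 0.95 / 40,000) ≈ 0.1 percentage point. Chance of at least one p < 0.05, as the range over correlation 0.3–0.9:

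| Tests allowed to count | 21 v 18 | 30 v 30 | 50 v 50 |
|---|---|---|---|
| One t-test at Week 48 | 5.0% | 4.9–5.1% | 4.8–5.1% |
| t-tests at Weeks 24 and 48 | 7.2–9.4% | 7.3–9.5% | 6.8–9.7% |
| Two t-tests, GEE, profile | 9.2–11.2% | 9.1–11.2% | 8.6–11.3% |
| Week 48 t-test, GEE, profile, survival | 11.3–12.2% | 10.9–12.3% | 10.4–12.2% |
| All four methods, both visits | 12.0–13.7% | 11.4–13.7% | 11.0–13.8% |

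Relative to 5%, the narrowest family is 6.8/5 = 1.4 to 9.7/5 = 1.9 times nominal, and the full family 11.0/5 = 2.2 to 13.8/5 = 2.8 times. An uncorrected robust GEE test raises the top of the full family to 14.3%, but part of that is small-sample bias in the estimator rather than multiplicity. Week 240 was left out because so few subjects can reach it.

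**The case against.** The strongest reply is that the synopsis does indicate a lead test. It assigns the arm difference to one two-sided t-test, and both places call GEE and profile analysis additional. That reading is fair, and a reader who inferred that the plan offers no hint of a lead test would be going too far. It does not close the gap. The synopsis never says the t-test decides, it names no visit, and Section 8.2.3 departs from it with plural t-tests and survival models.

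A second reply is that the inflation needs a rule that any one positive counts, and the plan states none. This also stands, so the percentages are conditional. But with no success criterion, nothing excludes that rule.

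A third is that the stakes are modest. Treatment effect is the last of three steps under a utility objective, and Section 6.6.3 bars management decisions based on the test. That limits the consequence but does not remove the need for a defined primary comparison.

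**Conclusion.** The concern holds in a bounded form. The treatment comparison has four methods, no named visit, no order and no multiplicity rule, and the synopsis and Section 8.2.3 disagree. If any one positive result counted, the false-positive chance would be roughly 7–14%: about 7–10% for t-tests at two visits and 11–14% for all four methods at both. This rests on the assumed correlation, test forms and arm sizes in the working.

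Three stronger readings are tempting, and the documents do not support them:
- *That the error rate is simply doubled.* No single multiple follows from the document; the figure depends on which tests count and on assumptions it does not supply. The 18.6% for four independent tests does not apply to shared data.
- *That Section 9 plans to cite a significant treatment difference in support of DSI as an endpoint.* It speaks of the overall results, which include histology, laboratory and outcome relationships, and does not mention significance.
- *That Week 240 adds materially.* Only 9 subjects, projected as 6 v 3, can reach it, and its contribution has not been quantified.

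The data remain usable. This should be corrected before unblinding.

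**What to change.** In Section 8.2.3 and the synopsis, in matching words, name one primary comparison: change in DSI from baseline to Week 48, selonsertib monotherapy versus placebo, two-sided 0.05. Week 48 is measured in all three trials and coincides with the histology comparators in Section 8.2.2. The two groups are those Section 8.2.3 already describes for the final analysis.

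ANCOVA adjusting for baseline DSI and F3/F4 stage is preferable, since this study measures the first and the parent trials' entry criteria fix the second. The planned t-test at Week 48 would cure the multiplicity equally well. Label Week 24, Week 240, GEE, profile and survival analyses as supportive.

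The cost is wording in two places, agreed with Gilead because Section 2.1 gives it these analyses, and completed before the code is broken. The downside is that a positive result at Week 24 or from another method could no longer be claimed as primary. Keeping both visits as co-equal with Bonferroni (0.025 each) is possible but dearer: 80% power for a difference of 2 at SD 3.5 needs 60 per arm, against 50 for a single two-sided t-test at 0.05.
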